## B. Experimental Participants

### 1. Recruitment of Veterans Presenting for Compensation examinations for PTSD:

The recruitment strategy involves identifying OEF/OIF/OND Veterans who have submitted requests for initial PTSD Compensation examinations.

Veterans applying for initial Compensation and Pension exams will be sent a letter by Express mail from [name] describing the study and notifying them that research staff will call with more information about the study in about six days. Up to three attempts will be made to contact the Veteran for recruitment before we will stop attempting. The letter will include a phone number to call to opt not to receive the research call. No phone calls will be made to Veterans calling to opt out.

We will also supply brochures and flyers to the Compensation and Pension office to make available to potentially eligible Veterans.

The reason to follow these recruitment procedures is that it is not feasible to recruit Veterans at the time they come for their Compensation examinations because the Veterans and examiners are too busy to complete the full research evaluations if they are recruited on-the-spot at the Compensation examinations, and the assessments are designed to be collected before the Compensation examination.

The proposed letter recruitment strategy, which was used in the QUERI study, a multi-site study of the Compensation and Pension process directed by [name], the Nashville site P.I. for this study, was effective. Of the 119 Veterans who were approached for study participation at West Haven, 16 who were called refused to participate and 10 returned opt-out letters, leaving the vast majority (n=93) who participated in this study. There were no adverse events associated with recruitment or with any of the study procedures. Most importantly, the QUERI study demonstrated Veterans' willingness to participate in a study of the Compensation process, even one that manipulated the very interview itself and involved audiotaping. It is noteworthy that only \$10 was provided for participation in the QUERI study (because it involved little additional time), and substantially more is being offered for participation in the proposed study.

### 2. Inclusion and Exclusion Criteria

#### a. Inclusion Criteria

---Veteran of OEF/OIF/OND?

---Not currently receiving VBA Compensation for PTSD

---Able to participate psychologically and physically, able to give informed consent and complete assessments, and participate in study procedures

---Between the ages of 18-65 years old.

b. Exclusion Criteria: Will not be able to attend the week 4 or 12 appointment because of anticipated incarceration or move

3. Criteria for Randomization to SBIRT or Control: All Veterans who complete the assessments and meet the substance abuse criteria (below) will be randomized except:

- Those who will not be able to attend the follow-up assessments because of planned incarceration or move
- Those enrolled in substance abuse treatment meeting three or more times per week.

The substance use criteria for randomization are:

**Either risky alcohol use OR self-reported use of an illicit drug within the last 28 days.**

- Risky alcohol use will be defined by standard criteria: >14 drinks/week or >4 drinks/occasion for men 65 or younger; >7 drinks/week or >3 drinks/occasion for women (Saitz 2005). A standard drink will be 0.5 oz of absolute alcohol, equivalent to 10 oz of beer, 4 oz of wine, or 1 oz of 100-proof liquor
- Self-reported use of an illicit drug on at least two days in the preceding 28 days.

*Veterans who use opioids will be eligible for randomization if any of the following apply to the opioids:*

- the opioids were not prescribed to the Veteran*
- *the Veteran describes obtaining the opioids from more than one provider (other than coordinated care)*
- *the Veteran endorses the SCID screening question indicating use of the drug for non-medical purposes (First, Spitzer et al. 1996)*

Veterans who use medical marijuana will be eligible for randomization. Justification: Veterans sometimes only use medical marijuana for medical reasons, sometimes use medical marijuana for reasons other than what it was prescribed for (e.g. to relax and not for pain relief), and sometimes have a medical prescription but also use marijuana from other sources. Regardless, medical marijuana use puts someone at risk for future misuse of cannabis or other drugs. Furthermore, medical marijuana is not legal in some states or federally. Randomized clients will be counseled about the risks if cannabis is used in ways other than how it is prescribed.

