### **Specific Aims**

The Compensation examination that determines if a Veteran is entitled to any disability payments related to military service is a crucial gateway to accessing VA care for returning OEF/OIF/OND Veterans. However, researchers and oversight agencies have noted that examiners typically do not have guidelines for evaluating comorbid conditions like substance abuse and for referring patients to treatment.

In the Evaluative Component of this study, OEF/OIF/OND Veterans presenting for Compensation evaluations for PTSD will be approached to undergo a paid battery of confidential substance use, PTSD, service use and attitude assessments prior to their scheduled Compensation examinations. The batteries will be collected again twice, four and twelve weeks after the Compensation examinations. Long-term follow-up data will be extracted from VA databases including diagnoses, the results of the Veterans' Compensation evaluations, award determination, use of VA services and attendance at mental health and/or substance abuse treatment.

In the Clinical Trial Component of this study, one hundred sixty Veterans identified during the baseline evaluation as having a substance use disorder will be randomly assigned to a session of Screening, Brief Intervention and Referral to Treatment (SBIRT) or to No-Additional-Treatment.

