#### Hypotheses for Evaluative Component:

1. Veterans with substance use disorders randomized to No-Additional-Treatment will have worse PTSD over time compared to Veterans without substance use disorders and will attend fewer weeks of mental health and/or substance abuse treatment, after accounting for baseline differences between substance users and non-users.
2. Attendance at treatment will be predicted by Veterans' perceptions that obtaining and maintaining VA benefits depends on attending PTSD treatment. Attendance at treatment will be negatively associated with the perception that VA benefits are more likely to be denied if a Veteran receives substance abuse treatment.
3. Long-term attendance at treatment (before Compensation exam to post-award notification) will be significantly impacted by the occurrence of the Compensation examination and determination of award. The effect of attitudes about how disability benefits are awarded will be significantly moderated by these time-varying covariates.

[figure not shown]

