#### **D. Research Design and Methods:**

## A. Design for the Proposed Evaluation and Clinical Trial Components

### Sampling of Patients with Substance Use and/or Risky Drinking:

The sampling frame will be the population of OEF/OIF/OND Veterans being evaluated at the participating sites for PTSD who are not already service-connected for it. We will use systematic sampling procedures to define the sample (Cochran, 1977), and will stratify the sample to ensure equal representation of patients from the Tennessee and Connecticut sites. A sampling interval will be estimated to achieve the recruitment rate, and extra recruiting will be included to account for Veterans who refuse to participate and/or are found to be ineligible after approach. The sampling interval will be adjusted after the first six months based on rates of participation from this phase. If the rate of participants meeting substance use criteria for randomization is below the anticipated rate of 25%, we will initiate a brief pre-screen for substance use prior to enrollment and oversample Veterans who pre-screen positive for substance use. This oversampling will allow for sufficient substance-using Veterans to be enrolled in the randomized clinical trial of SBIRT.

As is indicated in the Figure on the preceding page, all Veterans who screen positive for substance use disorders or risky alcohol use will be enrolled in the Clinical Trial Component. A conservative estimate was made that 160 veterans (25% of the sample) would be randomized to SBIRT or No-Additional-Treatment.

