Standard procedures will be employed to see that the delivery of the study therapy and the collection of study data are separated. The Evaluative Component and Clinical Trial Component will be carried out by a different staff member for each Veteran. After the data collector completes the assessments of the Veteran eligible for randomization, the data collector will enter the information for urn randomization into the computer program, but the study therapist will actually give the software command to conduct the urn randomization and generate group assignment. All outcome evaluations will be conducted by the data collector, and Veterans will be asked not to tell the data collector whether SBIRT was delivered. In summary, the clinical trial is not adversely impacted by the presence of a preceding Evaluative Component.

It also is unlikely that the Evaluative Component will not be interpretable because of the Clinical Trial Component. The 480 Veterans who are not randomized (because they do not have risky alcohol use and/or substance use) will be compared to the 80 substance users randomized to No-Additional-Treatment, using a prospective observational design to determine effects of substance use. Both groups will receive serial assessments that are not likely to impact outcomes.

2. Power Analysis for Analysis of the Effects of Substance Use on Outcomes: The effects of substance abuse on outcomes will be analyzed by random effects regression analyses. The treatment attendance outcome will yield a value for each week (attendance or not) and PTSD severity will be assessed at three time points (baseline, 4 and 12 weeks). In the primary analysis, these repeated-measures outcomes will be regressed on substance use, with covariates included that represent potentially confounding differences between Veterans with and without substance use disorders. The proposed sample of 560 participants receiving No-Additional-Treatment, of whom 80 are substance users, has power  $> .80$  to detect standardized mean differences in linear slopes as small as  $\delta = .25$ , allowing for potential downward bias in effects from nonrandom group assignment (Optimal Design software version 1.77), and partial  $\eta^2$  of  $< .1$ , correcting for non-sphericity (G\*Power 3.1.2, Buchner et al., 1992-2009).

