#### 4. Feasibility:

a. Feasibility of Identifying People Applying for Service Connection for Compensation Exams: At both VACT and TVHS, the Compensation and Pension Clinic schedules Veterans who apply for Compensation for examinations, making this clinic an efficient place to identify potential study participants. We have established procedures to recruit Veterans presenting for Compensation examinations in our previous studies.

b. Feasibility of Enrolling 480 Veterans in the Evaluative Component:

Tennessee: During 2009, TVHS was the site for 299 initial PTSD Compensation examinations for OEF/OIF Veterans, including 22 women.

VA Connecticut: After obtaining IRB approval, our group reviewed the VA charts and Compensation examination reports of 62 consecutive OEF/OIF Veterans who underwent Compensation examinations at VA Connecticut for the six-month period between 7/1/08 and 12/31/08 to estimate rates of substance use and service use. The fact that 62 OEF/OIF Veterans presenting for new PTSD examinations were examined during a six-month period at VA Connecticut, suggests a rate of 124 per year. According to CPRS, between 5/1/12-8/1/12 there were a total of 376 mental health exams scheduled of which 117 were for people not currently service-connected.

i. A rule-out or definitive diagnosis of alcohol abuse was made in eighteen Veterans and two additional Veterans had a substance abuse diagnosis for a total of 32% with an alcohol and/or substance abuse diagnosis. This likely underestimates the rates of substance use and risky drinking because chart review is an insensitive way to identify Veterans with substance use problems (Hawkins, Kivlahan et al. 2007). Only 3% of claimants had received any substance abuse treatment at VA during the three months before the evaluation and only 47% had received any mental health treatment. Altogether, 61% were diagnosed with PTSD on the Compensation examinations and 39% were not.

These results suggest that there is a high prevalence of substance use among OEF/OIF Veterans applying for PTSD-related Compensation, an unmet need for substance abuse treatment, and a range of PTSD-symptom severities.

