#### J. Data Analysis for Evaluative Component:

1. Sample Analyzed for Evaluative Component: The effects of substance abuse on outcomes will be analyzed in the sample of 560 participants who did not receive SBIRT, 80 of whom report risky alcohol/substance use and 480 who did not.

2. Data Reduction: Substance use disorder, PTSD diagnosis, and treatment attendance measures are being collected from more than one source. It is important to reduce the data prior to subsequent analyses to identify the outcomes that will be used in the analyses. These data reduction approaches are shown below:

a. The presence or absence of an Alcohol Use disorder at the time of the Compensation examination will be determined by the best estimate procedure developed by Spitzer and colleagues for validating DSM diagnoses (Spitzer, 1983). This procedure involves reviewing all available sources of information, which for this measure will include the SCID interview, Compensation examination report, substance use calendar, chart review and ICD-9 diagnoses.

A sensitive definition of alcohol use disorder will be employed, and the Principal Investigator will review all cases for which the Compensation Examination and SCID diagnosis are discordant. The reasons to use a sensitive but possibly less specific definition of alcohol use disorder are that an extensive literature documents that there are few "false positive" reports of alcohol and other substance abuse (Kosten and Rounsaville 1992). In a population of Veterans applying for PTSD-based disability, Veterans drinking substantial amounts of alcohol are likely to meet criteria for either Abuse or Dependence, and people with PTSD are particularly vulnerable to the psychological disruptions caused by drugs of abuse (Back, Brady et al. 2006). The same approach will be taken to arriving at best estimate diagnoses for other substances of abuse. The stability of the results will be determined by substituting alternate definitions of the substance use construct.

Descriptive analyses will be conducted to describe the agreement between the different sources of information. For example, the definition of alcohol-use disorders will be compared between the SCID Diagnoses during the assessment battery and the Compensation examinations. Preliminary descriptive and ROC analyses will be conducted of the accuracy of the Compensation examinations for determining alcohol use disorders with the validating criterion being the best estimate diagnosis.

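### The plan gives conflicting definitions of a substance user and treats every Veteran who is not randomized as a non-user, so the 480 comparators can include users.

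*Combined protocol and SAP*

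**What the plan says.** Five wordings describe the group of interest.

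- Specific Aims: "one hundred sixty Veterans identified during the baseline evaluation as having a substance use disorder will be randomly assigned". Evaluative Hypothesis 1, repeated in section J.4, follows suit: "Veterans with substance use disorders randomized to No-Additional-Treatment will have worse PTSD over time compared to Veterans without substance use disorders".
- Section A, on sampling, is wider: "all Veterans who screen positive for substance use disorders or risky alcohol use will be enrolled in the Clinical Trial Component".
- Section B.3, headline of the randomization criteria: "Either risky alcohol use OR self-reported use of an illicit drug within the last 28 days".
- Section B.3, drug bullet under that headline: "Self-reported use of an illicit drug on at least two days in the preceding 28 days". The alcohol bullet is set by amount: more than 14 drinks a week or 4 on an occasion for men, and more than 7 or 3 for women.
- Section J.2a: "The presence or absence of an Alcohol Use disorder at the time of the Compensation examination will be determined by the best estimate procedure", drawing on the SCID, examination report, calendar, chart and ICD-9 codes. Other substances are handled the same way. The section also promises to check whether results hold under other definitions.

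The comparator appears in section A, in the justification for combining the two components: "The 480 Veterans who are not randomized (because they do not have risky alcohol use and/or substance use". These Veterans are set against the 80 randomized controls, and section J.1 repeats the 80 and 480. Yet section B.3 also keeps out of randomization anyone who meets the use criteria but is already in substance abuse treatment three or more times a week. No section says where those Veterans are analyzed. Section J.4 tests substance use status by time without saying which definition sets the status.

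**The concern.** Not being randomized is a different thing from not using. Under the plan's own rules a user can end up unrandomized, and a randomized Veteran need not have a disorder. The Evaluative contrast may then compare mixed groups under a label (disorder versus no disorder) that matches neither. Two sites could also classify the same Veteran, with one day of drug use, in opposite ways. At stake are the size and direction of the Hypothesis 1 results and the population to which the trial's conclusion is attributed.

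**Working it through.** **Step 1. Reproduce the plan's counts.** Section A puts 160 randomized Veterans at 25% of the sample: 160 / 0.25 = 640. Then 640 - 160 = 480, and 480 + 80 = 560. All agree with the plan. The 480 is the remainder after randomization; it is not a count of Veterans shown to be non-users.

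**Step 2. Follow individual Veterans through the rules.**

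- Meets the use criteria and is in substance abuse treatment three or more times a week: not randomized under B.3, so in the remainder. This route does not depend on which wording governs.
- Has a best-estimate diagnosis but no drinking or drug use that reaches the B.3 thresholds: not randomized under B.3, although the sampling text in section A would enrol a Veteran who screens positive for a disorder.
- Used a drug on one day and does not drink riskily: randomized under the headline, in the 480 under the bullet.
- Man with one five-drink occasion and no disorder: randomized under B.3 and described in the aims and hypotheses as having a disorder.

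**Step 3. Effect on a standardized difference.** Let c be the share of the 480 who are users and d the share of the 80 who lack the condition in the hypothesis. If misclassified Veterans behave like their true group, observed difference = true difference x (1 - c - d). The documents give neither share, so the values below are assumptions.

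The Evaluative power statement claims power above .80 at 0.25. As a two-group approximation (two-sided 0.05 assumed), power is about Phi[0.25(1 - c - d) / SE - 1.96]. With 80/480, SE = sqrt(1/80 + 1/480) = 0.121 and power is 0.54. With an equal 280/280 split, SE = sqrt(2/280) = 0.085 and power is 0.84. Only the equal split comes out above .80. The plan does not give its slope-model inputs, so both columns are shown.

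| c (with d = 0) | Veterans of 480 | Observed difference | Power, 80/480 | Power, 280/280 |
|---|---|---|---|---|
| 0 | 0 | 0.25 | 0.54 | 0.84 |
| 5% | 24 | 0.2375 | 0.50 | 0.80 |
| 10% | 48 | 0.225 | 0.46 | 0.76 |
| 20% | 96 | 0.20 | 0.38 | 0.66 |

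Taking c = 10% and d = 10% together gives 0.25 x 0.80 = 0.20, the same as the last row.

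**Step 4. Effect on attendance.** Let t be the share of the 480 who are intensively treated users, attending mT weeks on average, while other comparators attend m0. The comparator mean rises by t x (mT - m0). Over an assumed 12-week window this is at most 12t, or 0.6 weeks at t = 5%. It moves toward the hypothesis that users attend fewer weeks. The only guide to t is the one-site chart review in section B.4, where 3% of claimants had VA substance abuse treatment in the prior three months. Even if all of them were in this group, 0.03 x 640 = 19.2, 19.2 / 480 = 4%, and 12 x 0.04 = 0.48 weeks. Non-VA treatment is not counted there.

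**The case against.** The strongest reply is that section J.2a does define disorder, from several sources and deliberately sensitively, and that J.4 tests substance use status, not randomization status. If the best-estimate diagnosis sets that status, diagnosed Veterans are moved to the right group. That is fair, but J.4 never says so. If it is so, the 80/480 split in sections A and J.1 no longer holds, because some randomized drinkers become non-cases. The check under other definitions helps only once a primary definition is named.

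Other points carry weight. Broad trial entry is deliberate and defended in section B. J.2a argues that heavy drinkers in this population probably meet diagnostic criteria. The B.3 headline can be read as a summary that the bullets define. Adjustment for baseline attendance and the focus on slopes in J.4 may remove part of the attendance bias. The Evaluative power statement allows for downward bias from nonrandom grouping, but it gives no amount and does not mention misclassification.

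A reader might infer that the 480 certainly contain Veterans with a disorder, and at least 45 of them. The feasibility review reports 20 of 62 claimants, "for a total of 32% with an alcohol and/or substance abuse diagnosis"; 0.32 x 640 = 204.8, less 160 leaves 44.8, or 9.3% of 480. The documents do not support this as a minimum. It subtracts a planning rate that section A calls conservative from a one-site chart rate that includes rule-out diagnoses. The 95% Wilson interval for 20/62 is about 22-45%, and 0.22 x 640 = 141 is already below 160. If more Veterans met the criteria, more would be randomized. A reader might also infer that B.3 ignores the SCID. It does use a SCID screening question, but only for opioids.

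**Conclusion.** Wrong as written. The definitions conflict on the face of the text, and the 80-versus-480 contrast does not test Hypothesis 1 as worded. The 480 can include users by the routes above; whether they do, and how many, the documents do not settle. On the assumption that misclassified Veterans behave like their true group, the PTSD difference shrinks by about the misclassified share, for example 5-10%. For attendance, intensively treated users counted as non-users push the result toward the hypothesis, by an amount that is probably small but unknown. The power figures are two-group approximations and show scale only. The randomized comparison of SBIRT with control is not biased by this, but its conclusion should not be attributed to Veterans with a disorder when the criteria select on use.

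**What to change.** 1. Make the illicit-drug threshold in the B.3 headline and bullet the same.
2. Name in J.4 one primary definition of substance use status. If it is the B.3 criteria, restrict the primary comparator to unrandomized Veterans with no risky alcohol use, no illicit drug use in the 28 days and no best-estimate substance use disorder under J.2a. Report all other unrandomized Veterans as a separate group, including those kept out because of treatment frequency.
3. Align the Specific Aims, the hypotheses and J.4 with that definition. Keep disorder as a pre-specified subgroup or as one of the alternate definitions promised in J.2a, and list those alternates.

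The cost is wording. The SCID and substance use calendar are already collected at baseline, and the other J.2a sources are already planned. The comparator becomes somewhat smaller, but the 80 users limit precision. If 10% were removed, 432 would remain and SE = sqrt(1/80 + 1/432) = 0.1217 against 0.1208, an increase of about 0.8%. If 20% were removed, 384 would remain and SE = 0.1229, an increase of about 1.8%.
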